5.2 Leukapheresis

- 5.2.1 PBMC will be harvested from the peripheral blood by a standard 1.5 to 2.0 blood volume mononuclear cell leukapheresis.
- 5.2.2 Mobilization with a colony-stimulating factor is not required.

5.3 Infusion

- 5.3.1 Confirm patient identity: APN401 is intended solely for autologous use. Confirm the proper product has been received according to the label on the outside of the insulated polyurethane container. Prior to APN401 infusion, match the patient's identity with the patient identifiers on the cell product disposition form and the APN401 infusion bag.

Safety and Immunologic Activity of Multiple Infusions of APN401

Wake Forest Baptist Comprehensive Cancer Center

CCCFWU 03716

- 5.3.2 Confirm expiration date and time: Infusion must begin prior to the expiration date and time indicated on the cell product disposition form and Product Label. **Do not initiate infusion of expired APN401.**
- 5.3.3 Inspect the infusion bag: Inspect the bag for signs of leakage. Do not administer if the bag leaks. Contents of the bag will be slightly cloudy, with a cream-to-pink color. Gently mix and re-suspend the contents of the bag, inspecting for clumps and clots. Small clumps of cellular material should disperse with gentle manual mixing. Do not administer if the bag leaks during handling or if clumps remain in the bag.
- 5.3.4 Vital signs will be recorded at screening, prior to infusion and at 30 and 60 minutes after infusion.
- 5.3.5 Administer APN401 via intravenous infusion over a period of approximately 30 minutes. **Do not use a cell filter.** The entire volume of the bag should be infused.
- 5.3.6 Observe the patient for at least 60 minutes following each infusion.

5.4 Supportive care guidelines

- 5.4.1 Patients should receive *full supportive care*, including transfusions of blood and blood products, antibiotics, antiemetics, etc. when appropriate. The reason(s), the drugs and dosage, and the dates of supportive treatments should be recorded on flow sheets.
- 5.4.2 Patients may receive the following to abrogate APN401 infusion toxicity:
 - Acetaminophen 650 mg po q 4 hr. May be given as pre-treatment at physician's discretion.
 - Hydroxyzine hydrochloride or diphenhydramine may be used for generalized erythematous rash. May be given as pre-treatment at physician's discretion.
 - Demerol 25-75 mg intravenously q 20 min can be administered concurrently to control chills and rigors.
 - Antiemetics and antidiarrheal agents as required.
- 5.4.3 Treatment with *hormones or other chemotherapeutic agents* may not be administered except for steroids given for pre-existing adrenal failure; hormones administered for non-disease-related conditions (e.g., insulin for diabetes). Use of dexamethasone and other steroid antiemetic or anti-inflammatory drugs is prohibited.
- 5.4.4 In the event of an acute infusion reaction, the infusion may be interrupted or slowed, depending on the severity of the reaction. Appropriate medical therapy should be administered as needed. If the infusion of APN401 must be interrupted, the infusion should not be resumed if the APN401 infusion bag will be held at room temperature for more than 3 hours.
- 5.4.5 APN401 is released for infusion based on the microbial and sterility results from several tests: microbial contamination determination by Gram stain, endotoxin content, and mycoplasma testing. Sterility sampling will be performed by the

Safety and Immunologic Activity of Multiple Infusions of APN401

Wake Forest Baptist Comprehensive Cancer Center

CCCFWU 03716

research technologist. APN401 is also cultured for microbial growth. The final (14-day incubation) sterility test results are not available at the time of infusion. If the sterility results become positive for microbial contamination after APN401 has been approved for infusion, the treating physician will be informed and testing to identify the microorganism as well antibiotic sensitivity testing on recovered microorganisms will be performed. The clinical investigator should evaluate the subject for any signs of infection that may be attributable to the product sterility failure. Additional information from the physician in order to determine the source of contamination may be necessary. See section 8.5.1 for the reporting requirement for sterility failure.

5.5 Nursing implications

- 5.5.1 It is important to maintain all scheduled appointments and arrive at each appointment on time because the leukapheresis and infusions must be appropriately spaced, and the APN401 expiration time must not be exceeded.
- 5.5.2 If the patient is unable to receive an infusion of APN401 within the required time, the patient will need to undergo an additional leukapheresis procedure if the treatment is to be continued.
- 5.5.3 Counsel the patient on the importance of adhering to preparation instructions for the leukapheresis procedure, the possible side effects of leukapheresis, and post-procedure care.
- 5.5.4 If the patient does not have adequate peripheral venous access to accommodate the leukapheresis procedure and infusion of APN401, inform the patient about the need for a central venous catheter. Counsel the patient on the importance of catheter care. Instruct the patient to tell their doctor if they are experiencing fevers or any swelling or redness around the catheter site, because these symptoms could be signs of an infected catheter.
- 5.5.5 Report signs and symptoms of acute infusion reactions such as fever, chills, fatigue, breathing problems, dizziness, high blood pressure, nausea, vomiting, headache, or muscle aches.
- 5.5.6 Report any symptoms suggestive of a cardiac arrhythmia.
- 5.5.7 Inform the treating doctor if the patient is taking immunosuppressive agents.

5.6 Duration of therapy

Patients will receive protocol therapy unless:

- 5.6.1 Extraordinary medical circumstances: If at any time the constraints of this protocol are detrimental to the patient's health, protocol treatment should be discontinued. This includes any clinical adverse event, laboratory abnormality or intercurrent illness which, in the opinion of the investigator, indicates that continued treatment with study therapy is not in the best interest of the subject.

Safety and Immunologic Activity of Multiple Infusions of APN401

Wake Forest Baptist Comprehensive Cancer Center

CCCWU 03716

- 5.6.2 Patient withdraws consent
- 5.6.3 Pregnancy: All WOCBP should be instructed to contact the investigator immediately if they suspect they might be pregnant (e.g., missed or late menstrual period) at any time during study participation. Pregnancy tests should be conducted as clinically indicated.
- 5.6.4 Disease progression: Patients who progress clinically before week 9 will be removed from study if other therapy (surgery, radiation, chemotherapy) is needed urgently.

When a patient is removed from study, the Off-Study Form/Early Termination must be completed within seven days.

5.7 Duration of follow-up

All patients, including those who discontinue protocol therapy early, will be followed for response until progression or one year from registration, whichever occurs first. Patients will then be followed for survival for five years from the date of registration. All patients must also be followed through completion of all protocol therapy.

Safety and Immunologic Activity of Multiple Infusions of APN401
Wake Forest Baptist Comprehensive Cancer Center
CCWFU 03716

6.0

Study Calendar

Baseline evaluations, including imaging, are to be conducted within 4 weeks prior to initiation of treatment (Day 0). In the event that the patient's condition is deteriorating, laboratory evaluations should be repeated within 48 hours prior to initiation of the next cycle of therapy.

		Treatment Phase							Follow-Up Phase		Early Termination
	Pre-Study ^J	Day 0 Week 1	Day 1 Week 1	Day 15 Week 3 (± 1 day)	Day 28 Week 5 (± 3 days)	Day 29 ^N Week 5	Day 56 Week 9 (± 3 days)	Day 57 ^N Week 9	Day 71 Week 10 (± 3 days)	Week 18 and every 8 weeks (± 1 week) ^L	Off Study Visit/Early Termination Visit ^{L,M}
Leukapheresis ^A		X			X		X				
APN401 ^B			X			X		X			
Informed consent	X										
Demographics	X										
Medical history	X										
Concurrent meds		X			X		X		X	X ^O	X
Vital signs ^C	X	X	X	X	X	X	X	X	X	X	X
Physical exam ^Q	X	X		X	X		X		X	X	X
Performance status	X	X		X	X		X		X	X	X
CBC w/diff ^D	X	X		X	X		X		X	X	X
Chemistries ^E	X	X		X	X		X		X	X	X
PT, PTT	X										
HIV, HBV, HCV	X										
βhCG ^F	X										
Adverse events		X	X	X	X	X	X	X			X
Imaging ^G	X								X ^L	X ^K	X ^L
Tumor marker ^H	X								X	X	X
Immune response ^I		X		X	X		X			X	X

A. PBMC will be harvested from the peripheral blood by a standard 1.5 to 2.0 blood volume mononuclear cell leukapheresis.

B. APN401 is infused 50 x10⁵/kg IV over 30 minutes

C. Vitals signs should include blood pressure, heart rate, temperature, and respiratory rate. At the administration visits, vital signs should also be performed before infusion and 30 and 60 minutes after the end of the infusion.

D. Hemoglobin, hematocrit, white blood cell count, and platelets. The CBC differential includes enumeration of neutrophils, lymphocytes, eosinophils, monocytes, basophils and any abnormal blood cells.

E. Serum albumin, urea or BUN, creatinine, ALT, AST, LDH, alkaline phosphatase, direct and total bilirubin, glucose, total protein, sodium, potassium, chloride, CO₂, calcium, phosphorus, and uric acid. These labs should be obtained less than 36 hours prior to the treatment.

F. Women of child bearing potential must have a negative serum or urine pregnancy test (minimum sensitivity 25 IU/L or equivalent units of HCG) at screening. A pregnancy test should also be obtained at any time if there are clinical concerns for possible pregnancy.

G. Imaging should include a chest and abdomen CT. Other types of imaging and/or imaging of other sites should be obtained as clinically indicated to document extent of cancer. If restaging imaging indicates partial or complete response, repeat confirmatory imaging should be obtained in 4 weeks (but

Safety and Immunologic Activity of Multiple Infusions of APN401
Wake Forest Baptist Comprehensive Cancer Center
CCCFU 03716

no sooner than 4 weeks).

H. CA19-9 in patients with pancreatic cancer, CEA in patients with colorectal cancer, and other standard-of-care tumor markers as clinically indicated.

Repeat assessment not required if completed within 2 months of pre-study or early termination visit.

I. On Days 0, 28 and 56, the immune response testing will be taken from the leukapheresis product. On Day 15 and in the follow-up phase, collect 30 ml of blood (3 vials) into 10 ml EDTA tubes. If immune response labs have been collected within 4 weeks prior to the off study/ termination visit, re-collection is not required.

J. Peripheral blood laboratory studies performed in order to determine patient eligibility must be performed within 28 days of study entry. Radiographic and other tests performed in order to determine patient eligibility must be performed within 28 days of study entry.

K. Follow-up radiologic procedures used to assess outcome should be performed within 7 working days of the scheduled time.

L. Patients will be observed until objective disease progression or 1 year, whichever occurs first.

M. Off study/early termination assessments are only indicated for patients who do not complete all study visits (until week 58) /Follow-Up phase. These assessments should occur no more than 4 weeks after the discontinuation of study treatment. If the subject had not undergone imaging within the past 6 weeks re-imaging is indicated. If a patient discontinues treatment for any reason other than progression, imaging will be done every 12 weeks until progression.

N. Must occur the day following leukapheresis day.

O. Following the week 18 visit only documentation of anti-cancer treatment.

P. Adverse events will be recorded on an ongoing basis and up to 2 months following the administration of the test drug.

Q. Physical Exam may be completed +/- 2 days of visit.

Safety and Immunologic Activity of Multiple Infusions of APN401
Wake Forest Baptist Comprehensive Cancer Center
WFBCCC 03716

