1.4 Phase 1 study of single infusion of APN401

The feasibility and safety of a single intravenous infusion of APN401 were evaluated in patients with refractory metastatic solid tumors [14]. Patients with active autoimmune disease or a requirement for immune suppressive drugs were excluded. PBMC were collected by leukapheresis. The following day PBMCs were transfected with Cbl-b siRNA by electroporation to produce APN401 and then infused intravenously over 30 minutes. Three to ten patients were treated in each of the three dosing cohorts in which they received a single intravenous infusion of 5, 10, or 50×10^5 cells/kg APN401. PBMC were successfully collected and transfected with Cbl-b siRNA in all patients enrolled. CD3 T cell, CD56 NK cell, CD19 B cell, and CD14 monocytes were transfected with similar efficiencies. Transfected PBMCs produced 4-fold more IFN- γ 2-fold more IL-2 in response to CD3/CD28 stimulation than PBMC that were processed and electroporated without siRNA. From 27.0 to 467×10^6 siRNA transfected PBMCs were infused. Infusions were well tolerated. Mild to moderate chills developed in most patients at the completion of the infusion. Dose-limiting toxicities were not observed. There was no immediate hypersensitivity and no evidence of autoimmune adverse effects. Stable disease observed in two patients with pancreatic cancer and one with colorectal cancer was associated with increases in PBMC responses to stimulation with CD3/CD8 and tumor-associated peptides.

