1.5 Study rationale

Adoptive cellular immunotherapy with ex vivo manipulated autologous immune cells has been an attractive approach to refractory cancers. Cbl-b is a major negative regulator of immune function. Adoptive cellular immunotherapy with Cbl-b silenced cells significantly

Safety and Immunologic Activity of Multiple Infusions of APN401

Wake Forest Baptist Comprehensive Cancer Center

CCCWU 03716

decreased tumor burden in mouse models without toxicity. Multiple infusions were applied in these studies. APN401 is a suspension of autologous human PBMCs transfected *ex vivo* with a siRNA that silences Cbl-b developed for adoptive cellular immunotherapy applications. A phase I clinical trial to determine the toxicities of a single intravenous administration of APN401 established feasibility and safety. This clinical trial will examine multiple infusions and also provide an initial estimate of immunologic activity. The overall goal is to determine if there is sufficient evidence of safety and immunologic activity to proceed to phase II clinical trials, alone or in combination with other antitumor agents.

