5.0 Treatment Plan

5.1 Dosing

- 5.1.1 Leukapheresis to collect PBMC for infusion will be performed the day prior to infusion. Patients will be administered three infusions of APN401 at 50×10^6 cells/kg IV, separated by 4 weeks (reference Appendix I). Leukapheresis and administration of APN401 can be delayed up to 3 weeks at the physician's discretion. Subsequent treatment must occur 28 days after prior treatment.
- 5.1.2 Six patients will be treated initially. Should >1/6 subjects experience greater than grade 3 or 4 toxicity, further enrollment of study subjects and further administration of the study agent will stop pending assessment of the risk.
- 5.1.3 If DLT is observed in $\leq 1/6$, than an additional four patients (a total of 12) will be enrolled to allow evaluation of laboratory correlates. Enrollment will be suspended if >1/6 or >3/12 patients manifest DLT

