7.3 Side effects

Infusions of APN401 have been well tolerated. Grade 3 or 4 toxicities attributable to treatment were not observed. Chills are the most common toxicity. These manifested at the completion of the 30 minute infusion and responded to meperidine. Transient lymphopenia, attributed to the leukapheresis, was also observed. Anemia, anorexia, dyspnea, fatigue, fever, hyponatremia, nausea, and myalgia have also been observed.

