7.5 Administration

APN401 is administered at 50×10^6 /kg via intravenous infusion over a period of approximately 30 minutes. **Do not use a cell filter.**

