7.6 Cell Processing

Cell processing is performed in the Blood and Bone Marrow Transplant Lab in the North Tower at WFBMC. The BMT lab is not accredited for this purpose and does not have responsibility for the procedures as part of this study within the laboratory. The research team, which includes the PI and an experienced technician, is responsible for the safety, purity and potency of the cellular products under protocol.

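### The protocol gives the APN401 dose as 50 × 10⁶ cells/kg in two sections and 50 × 10⁵ cells/kg in the Study Calendar, a tenfold conflict that nothing in the document resolves

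*Combined protocol and SAP*

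**What the plan says.** The dose for this trial is stated in three places.

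- Section 5.1.1 (Dosing): "Patients will be administered three infusions of APN401 at" 50 × 10⁶ cells/kg.
- Section 7.5 (Administration): "APN401 is administered at" 50 × 10⁶ per kg.
- Section 6.0, Study Calendar, footnote B: "APN401 is infused 50 x10⁵/kg IV over 30 minutes".

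Section 1.4 describes the earlier single-infusion study, with three cohorts "in which they received a single intravenous infusion of 5, 10, or" 50 × 10⁵ cells/kg, totals of 27.0 to 467 × 10⁶ cells infused, and no dose-limiting toxicity. Section 1.5 relies on that study for feasibility and safety and describes what is new: "This clinical trial will examine multiple infusions and also provide an initial estimate of immunologic activity". It mentions no increase in dose.

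Other places where the question might be settled do not settle it. The synopsis and Section 7.2 give no cell number. The dosing sentence in 5.1.1 points to Appendix I, which is a data form for flow cytometry counts.

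**The concern.** The trial's purpose is to establish whether repeating an infusion is safe, and single-dose safety is taken from the study in Section 1.4. That argument holds only if the dose is the one already tested. On the figure in 5.1.1 and 7.5, the first six patients would instead enter an undeclared tenfold escalation, given three times. The reassurance in Section 7.3, "Grade 3 or 4 toxicities attributable to treatment were not observed", would not cover that dose.

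Mixed dosing between patients is not the main risk. This is one centre, and under Section 7.6 one research team "is responsible for the safety, purity and potency of the cellular products under protocol". The main risk is that a single misreading carries through to every product. Section 5.3.5 says "The entire volume of the bag should be infused", so an error in preparation reaches the patient in full. Even if all products are consistent, the reported toxicity rate cannot be tied to a known dose while the protocol gives two.

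**Working it through.** **Inputs.** This trial's dose: 50 × 10⁶/kg (5.1.1, 7.5) and 50 × 10⁵/kg (footnote B). Earlier cohorts: 5, 10 and 50 × 10⁵/kg (1.4). Earlier totals: 27.0 × 10⁶ to 467 × 10⁶ cells (1.4). Body weights are not given, so 50, 70 and 100 kg are assumed below.

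**Step 1. Size of the conflict.** 50 × 10⁶ / 50 × 10⁵ = 10.

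**Step 2. Is the 10⁵ in Section 1.4 right?** The totals test the exponent, because implied weight = total cells / (cells per kg). This assumes that full nominal doses were given and that the patients were adults.

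| Total infused | Cohort | Implied weight, 10⁵ scale | Implied weight, 10⁶ scale |
|---|---|---|---|
| 27.0 × 10⁶ | 5 | 54 kg | 5.4 kg |
| 27.0 × 10⁶ | 10 | 27 kg | 2.7 kg |
| 27.0 × 10⁶ | 50 | 5.4 kg | 0.54 kg |
| 467 × 10⁶ | 5 | 934 kg | 93.4 kg |
| 467 × 10⁶ | 10 | 467 kg | 46.7 kg |
| 467 × 10⁶ | 50 | 93.4 kg | 9.34 kg |

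We do not need to know which cohort produced which total. On the 10⁵ scale, the smallest total implies at most 54 kg and the largest at least 93.4 kg. Both are plausible adult weights, and they arise in the lowest and highest cohorts, as one would expect. On the 10⁶ scale, the smallest total needs a patient of at most 5.4 kg. In addition, everyone in the top cohort received at most 467 × 10⁶ cells and so would weigh at most 9.34 kg. The earlier study was therefore on the 10⁵ scale, and its top dose was 50 × 10⁵/kg.

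**Step 3. What each stated dose means for a patient.** Cells per infusion = dose per kg × weight. The ratio is to the earlier maximum of 467 × 10⁶.

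| Assumed weight | At 50 × 10⁵/kg | Ratio | At 50 × 10⁶/kg | Ratio |
|---|---|---|---|---|
| 50 kg | 250 × 10⁶ | 0.54 | 2,500 × 10⁶ | 5.35 |
| 70 kg | 350 × 10⁶ | 0.75 | 3,500 × 10⁶ | 7.49 |
| 100 kg | 500 × 10⁶ | 1.07 | 5,000 × 10⁶ | 10.71 |

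Over three infusions at 70 kg, the cumulative totals are 3 × 350 = 1,050 × 10⁶ and 3 × 3,500 = 10,500 × 10⁶ cells.

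**Step 4. Which figure fits the rest of the protocol?** The lower figure equals the top cohort already tested and keeps per-infusion totals close to the earlier range. It also agrees with Section 1.5, where the only new element is repetition. The higher figure repeats the number 50 with a different exponent and has no supporting text.

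**The case against.** The strongest reply is that the documents do not show which dose is intended. Within this trial's own instructions, two operative sections give 10⁶ and one calendar footnote gives 10⁵. Section 1.4 establishes the earlier study's dose, not this one's. Section 1.5 contains no dose, so its support is indirect. This stands: the lower figure is the better supported reading, not a proven one.

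The whole conflict is also one superscript digit, and a misprint or misreading cannot be fully excluded. But 10⁶ appears in two separate sections, and the cell totals confirm the 10⁵ in Section 1.4 independently. If footnote B alone were wrong, an unexplained tenfold step above the tested range would remain.

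Third, Section 1.1 says processing follows SOPs, and those may fix the dose correctly in practice. The reference in 5.1.1 to Appendix I may point to an appendix since re-lettered, as Section 10.2 also cites appendix letters that do not match the current list. Both are possible. Neither source is in the protocol, so the protocol still contradicts itself.

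Finally, the review after six patients and the suspension rule for dose-limiting toxicity give some protection at the higher dose. They limit harm once toxicity appears; they do not justify starting there. It is also fair to set aside the cumulative three-infusion totals when comparing with a single-infusion maximum. The per-infusion ratios are the relevant ones.

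**Conclusion.** The concern holds. The protocol states two doses for the same infusion, ten times apart, and nothing in it says which governs. At 50 to 100 kg the choice is between 0.5 to 1.1 times and 5.4 to 10.7 times the largest number of cells previously given in one infusion. The conflict itself rests on no assumption. The size in cells rests on the assumed weights, and the confirmation of the 10⁵ scale in Section 1.4 rests on full nominal dosing of adults. The evidence points to 50 × 10⁵/kg without settling it. If 50 × 10⁶/kg is intended, the protocol contains an unjustified tenfold escalation. A correction is needed in either case, and because it concerns the administered dose it must be made.

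**What to change.** First confirm the intended dose against the cell-processing SOP. If it is 50 × 10⁵ cells/kg, as the evidence suggests, change Sections 5.1.1 and 7.5 to match footnote B and the top cohort in Section 1.4. If 50 × 10⁶ cells/kg is truly intended, correct footnote B and add a justification for going tenfold above the highest tested dose. Correct the Appendix I reference in 5.1.1 at the same time.

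In either case, record the cells/kg actually infused for each patient at each infusion and report toxicity against it. The fields of the product disposition form are not reproduced in the protocol, so this value may already be captured; if so, only the reporting needs adding.

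The cost is one text correction, one check against the SOP and at most one extra recorded value per infusion. It needs no additional patients or procedures.
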